If 2 or more patients experience a DLT at Dose Level 0, the MTD will be declared at 45 mg, which was the MTD established in the previous phase I study in patients with advanced glioma with a QD dosing schedule. On the basis of the review of real-time safety data and available preliminary PK data from this study with GDC-0084, dose-escalation may be halted or modified by the sponsor as deemed appropriate.

Decisions regarding dose-escalation and selection will be made by a CRC including the medical monitor, recruiting Investigators, sponsor representative and any other relevant and necessary expert on as needs basis, according to the CRC charter.

Definition of Dose Limiting Toxicity

All AEs, including DLTs, will be reported, with severity assessed according to National Cancer Institute (NCI) Common Terminology Criteria for Adverse Events (CTCAE), version 4.03. For dose-escalation purposes, DLT assessments will be performed by the sponsor in consultation with the Investigators during the CRC meetings.

A DLT is defined as any one of the following toxicities occurring within the DLT assessment window (Cycle 1, Days 1–28) and assessed by the Investigator to

Version: Amendment 4 Date: 31 Mar 2020

IND Number: 112.608

be probably or possibly related to GDC-0084:

Grade ≥ 3 non-hematologic or non-hepatic toxicity that is not related to hyperglycemia or hyperlipidemia or mucositis/stomatitis and is not due to disease progression or another clearly identifiable cause, excluding the following:

Protocol Number: NVGN-0084-201

- Alopecia of any grade;
- o Grade 3 fever or Grade 4 fever < 5 days duration;
- o Grade 3 infection < 5 days duration or that responds to treatment:
- Grade 3 weight gain or loss;Grade 3 diarrhea lasting less than 5 days or that responds to standard-of-care therapy including hospitalization
- o Grade 3 nausea or vomiting, in the absence of premedication, that lasts for less than 48 hours or responds to standard-ofcare therapy:
- o Grade 3 or asymptomatic Grade 4 electrolyte imbalance that resolves or improves within 7 days with or without medical intervention, including hospitalization;
- Grade 3 or 4 serum amylase or lipase or creatine phosphokinase laboratory abnormality that is asymptomatic (without other laboratory evidence suggestive of pancreatitis, rhabdomyolysis, or other major organ dysfunction) and returns to baseline within 7 days of interrupting study drug:

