Protocol Number: NVGN-0084-201 Version: Amendment 4 IND Number: 112,608

Dose-Escalation Rules

Dose-escalation will occur in Stage 1:

The initial dose (Dose Level 0) for QD MTD determination in will be 60 mg. Dose levels will increase in 15 mg steps:

- The dose-escalation portion of the study (Stage 1) will use a "3 + 3" design to assess the safety, tolerability, and PK of GDC 0084 administered orally in 28-day cycles:
- Each dose cohort will initially enroll 3 patients. If none of these patients experiences a DLT within the DLT assessment period (Day 1 - 28), escalation will proceed to the next higher dose level by opening the next higher dose cohort with newly recruited patients;
- If 1 patient experiences a DLT, the cohort will be expanded until a second patient experiences a DLT or to a maximum of 6 patients. When a second patient has a DLT, the MTD is determined as 1 dose level below the current dose level; i.e. the highest dose level at which less than 1/3 of patients (e.g. 1 of 6) experiences a DLT will be declared the MTD.
- If 2 or more patients experience a DLT at Dose Level 0, the MTD will be declared at 45 mg, which was the MTD established in the previous phase I study in patients with advanced glioma with a QD dosing schedule.

On the basis of the review of real-time safety data and available preliminary PK data from this study with GDC-0084, dose-escalation may be halted or modified by the sponsor as deemed appropriate.

Decisions regarding dose-escalation and selection will be made by a CRC including the medical monitor, recruiting Investigators, sponsor representative and any other relevant and necessary expert on as needs basis, according to the CRC charter.

Definition of Dose Limiting Toxicity

All AEs, including DLTs, will be reported, with severity assessed according to National Cancer Institute (NCI) Common Terminology Criteria for Adverse Events (CTCAE), version 4.03. In case a patient experiences one of the below, study participation will be terminated for this patient and the EoT visit should be performed.

For dose-escalation purposes, DLT assessments will be performed by the sponsor in consultation with the Investigators during the CRC meetings.

A DLT is defined as any one of the following toxicities occurring within the DLT assessment window (Cycle 1, Days 1 - 28) and assessed by the Investigator to be probably or possibly related to GDC-0084:

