- Mucositis/stomatitis Grade 3 not responding to standard-of-care therapy or Grade 4. Sites should consider using an alcohol-free dexamethasone 0.5 mg per 5mL oral solution (elixir) if such symptoms eventuate. Patients may be instructed to use 10ml oral solution swished for up to two minutes and then spit, up to four times daily (Rugo et al. 2017).
- Decrease in left ventricular ejection fraction (LVEF) to ≤ 45%;
- Increase of QTc to ≥ 500 msec or by 60 msec:
- Pneumonitis Grade ≥ 2.

After determination of the MTD, patients continue to receive their protocol assigned dose levels of GDC-0084 until progression of their disease or an unacceptable toxicity, whichever occurs first.

Patients who experience disease progression or an unacceptable toxicity at any time during the study, or, in their opinion or the opinion of the Investigator, are not benefiting from GDC-0084, will be discontinued from study treatment. Under certain circumstances in which an AE (or DLT) is reversible and the risk/benefit assessment suggests a reasonable rationale for continued administration of study drug, patients may continue with agreement from the Investigator and the medical monitor. This may include dose reduction and change of treatment schedule. An End of Treatment visit will be performed approximately 28 days after the last dose of GDC-0084.

3.7.2 Stage 2

Stage 2 of the study will be a two-arm, randomized, open-label expansion cohort to further characterize safety, tolerability and PK of GDC-0084 when administered QD in 28-day cycles, and to explore the effect of food on the PK of GDC-0084, as well as to provide a preliminary assessment of single-agent activity of GDC-0084 in patients with GBM.

The expansion will start with a screening period, followed by treatment and follow-up periods. It will be initiated with recruitment of new patients as soon as the MTD for QD dosing has been determined.

Approximately 20 patients will be enrolled in the expansion cohort according to the defined study eligibility criteria, to perform the comparison of safety and clinical activity. On Days 1 and C2D1, 10 patients will receive GDC-0084 in a fed state, while the remaining 10 patients will receive GDC-0084 in a fasted state. Patients will be allocated to either fed or fasted arms via a central randomization mechanism.

Patients enrolled in Stage 2 may continue the study at the dose allocated until disease progression or unacceptable toxicity.

Version: Amendment 4 Date: 31 Mar 2020

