4.6.12 Follow-up Visits

There is a short-term follow-up visit 28 days after end of study treatment (last dose). There is longterm follow-up performed by telephone conversation or site visit (depending on practical considerations) where all patients in Stage 1 and Stage 2 who discontinue study treatment will be followed every 8 weeks until determination of progressive disease (PD) and then until death unless the patient requests to be withdrawn from survival follow-up or termination of the study by the Sponsor. This request must be documented in the source documents and signed by the Investigator.

Duration of Therapy

After the screening period of up to 28 days, patients start to take GDC-0084 in 28-day cycles (every day continuous dosing is intent). Dose and regimen depend on the study stage and findings during the study (see Section 3.7 and Section 4.4.1).

In the absence of treatment delays due to AEs, treatment may continue until 1 of the following criteria applies:

- DLTs (Stage 1, Cycle 1);
- Disease progression;
- Intercurrent illness that prevents further administration of treatment:

Version: Amendment 4 Date: 31 Mar 2020

IND Number: 112.608

- Patient decides to withdraw from the study;
- General or specific changes in the patient's condition that render the patient unacceptable for further treatment in the judgment of the Investigator.

Protocol Number: NVGN-0084-201

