4.9 Dose Delays and Dose Modifications

4.9.1 **Retreatment Criteria**

Prior to proceeding to the next cycle, patients must have recovered the following organ function:

- Absolute neutrophil count $\geq 1.5 \times 10^9 / L$;
- Platelets $\geq 100 \times 10^9 / L$;
- Total bilirubin within normal institutional limits;
- AST/ALT ≤ 2.5 X institutional ULN.

Laboratory evaluations must be performed within 48 hours prior to initiation of each cycle of therapy. Patients not fulfilling these criteria should have treatment delayed until the recovery of organ function. Patients who cannot be retreated within 2 weeks of the end of the previous cycle should be removed from study.

4.9.2 **Dose Modification Guidelines**

In general, dose modifications are not foreseen during the study. However, under certain circumstances in which the risk/benefit assessment suggests a reasonable rationale for continued treatment with GDC-0084, e.g., after an AE (or DLT), patients may continue with a reduced dose or a change of treatment schedule if the Investigator and medical monitor agree.

Patients in Stage 1 will be enrolled to their allocated dose at a QD dosing frequency. They will continue to receive study drug based on the cohort to which they are assigned, and intra-patient dose escalation is not permitted. Dose reduction is permitted if clinically indicated.

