4.11.2 Definition of Dose-Limiting Toxicity

Toxicities will be graded according to the NCI CTCAE v4.03. If a patient experiences one of the below, study participation will be terminated for this patient and the EoT visit should be performed.

For dose-escalation purposes, DLT assessments will be performed by the Kazia Therapeutics Limited in consultation with the Investigators during CRC meetings. A DLT is defined as any one of the following toxicities occurring within the DLT assessment window (Cycle 1, Days 1 - 28) and assessed by the Investigator to be related to GDC-0084.

Details on DLTs are given in Section 3.7.1.

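### The rules for treatment after a DLT disagree on whether and how dosing may continue, and ending study participation conflicts with the planned follow-up

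*Combined protocol and SAP*

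**What the plan says.** Three places in the combined protocol and SAP make a DLT a stopping event.

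- Section 3.7.1, Definition of Dose Limiting Toxicity: for a patient with a listed event, "study participation will be terminated for this patient and the EoT visit should be performed".
- Section 4.11.2: "If a patient experiences one of the below, study participation will be terminated for this patient and the EoT visit should be performed". It then refers back: "Details on DLTs are given in Section 3.7.1".
- Duration of Therapy (between 4.6.12 and 4.8): the first listed criterion that ends treatment is a DLT in Stage 1, Cycle 1.

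Two places let treatment go on.

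- Closing paragraph of 3.7.1: "Under certain circumstances in which an AE (or DLT) is reversible and the risk/benefit assessment suggests a reasonable rationale" for continued dosing, "patients may continue with agreement from the Investigator and the medical monitor". The next sentence says this may include a lower dose and a different schedule.
- Section 4.9.2: where risk/benefit supports it, for example "after an AE (or DLT), patients may continue with a reduced dose or a change of treatment schedule", again if the Investigator and medical monitor agree.

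On follow-up, 4.6.12 and 4.8 (and the synopsis) require 8-weekly contact with all Stage 1 and Stage 2 patients who stop treatment, to progression and then to death. The only exits named are the patient's request and termination of the study by the sponsor. Section 4.9.1 says that a patient who cannot be retreated within 2 weeks of the end of the previous cycle should be removed from study.

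**The concern.** The stop sentences contain no exception and do not mention 4.9.2, and the two permissive texts do not state the same exception. An investigator with a patient who has had a DLT can find support in the protocol for stopping, for continuing at the same dose, or for continuing only at a lower dose or on another schedule. The DLT list includes myocardial ischemia, an LVEF of 45% or less, QTc prolongation and pneumonitis, so the terms for re-dosing are a real safety question.

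The second issue concerns data. The protocol elsewhere treats stopping the drug and leaving the study as different things: 4.5.2 names discontinuation of GDC-0084 and study withdrawal separately. Taken literally, ending participation at a DLT would end PFS and OS follow-up in Stage 1 patients because of toxicity. These patients belong to the safety population, in which 6.3.4 places the primary Stage 1 PFS analysis.

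**Working it through.** No figure in the plan bears on this point, so the check compares texts.

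**Step 1: what each place allows after a DLT**

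| Place | Treatment may continue? | Event must be reversible? | Lower dose or changed schedule required? | Who must agree |
|---|---|---|---|---|
| 3.7.1, DLT definition | No | – | – | – |
| 4.11.2 | No | – | – | – |
| Duration of Therapy | No (Stage 1, Cycle 1) | – | – | – |
| 3.7.1, closing paragraph | Yes | Yes | No, optional | Investigator and medical monitor |
| 4.9.2 | Yes | Not stated | Yes, the only form provided for | Investigator and medical monitor |

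Both permissive texts also require a risk/benefit rationale. They differ on reversibility and on whether the dose or schedule must change.

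**Step 2: two test cases**

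- *Reversible DLT, continuation at the assigned dose proposed.* The stop sentences say no. The closing paragraph of 3.7.1 allows it with agreement. Section 4.9.2 provides only for a reduced dose or changed schedule.
- *DLT that has not reversed, for example an LVEF that stays at 45% or below, with a lower dose proposed.* The stop sentences say no, and the closing paragraph of 3.7.1 does not cover it. Section 4.9.2 permits it if risk/benefit supports it and both parties agree.

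Reading the permissive texts as exceptions settles that some continuation is possible. It settles neither case, because the exceptions give different answers.

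**Step 3: participation against follow-up**

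Sections 4.6.12 and 4.8 cover every patient who stops treatment, and a DLT is not among their exits. A patient whose participation has ended cannot also be followed every 8 weeks to progression and death. The same applies to a patient removed from study under 4.9.1.

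On the literal reading, a Stage 1 patient with a DLT would be handled as follows:

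1. The DLT falls in Days 1–28. The first scheduled on-treatment MRI is at Week 8 (4.6.3).
2. Table 1 schedules an MRI at the End of Treatment visit. Without progression or death, PFS would be censored there or, with no post-dose scan, at Day 1 (6.3.4).
3. OS would be censored at the date last known alive, with no later planned contact. The reason for censoring would be toxicity.

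**Step 4: what does not change**

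The 3 + 3 rules count patients with a DLT in Cycle 1. What happens to the patient afterwards does not alter that count. Section 4.3.1 allows replacement only for patients who discontinue for reasons other than safety, so a DLT patient is not replaced. Escalation and the MTD follow from the count.

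**The case against.** The best defence is that the plan states a general rule and a named exception. The closing paragraph of 3.7.1 is in the same section as the stop sentence and names DLTs, 4.9.2 names them again, and 4.11.2 sends the reader to 3.7.1. If the stop were absolute, naming DLTs in the permissive texts would mean nothing. This is probably the intent, and it stands as far as it goes. It does not explain why the two statements of the exception differ.

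A reader might infer that sites can handle the same DLT as they please. The documents do not support that: both permissive texts require the medical monitor's agreement, the medical monitor sits on the Cohort Review Committee, and the sponsor assesses DLTs with the Investigators at its meetings. What remains is that the medical monitor has two sets of conditions to apply.

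A reader might also infer that follow-up of DLT patients will be lost. That too goes beyond the text. The stop sentence is tied to the End of Treatment visit, the closing paragraph of 3.7.1 speaks of stopping study treatment, and the rule to follow all such patients appears three times, counting the synopsis. The likely intent is to stop treatment. The loss arises only on a literal reading, but the words do say participation.

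**Conclusion.** The point holds as a conflict between stated rules. The plan does not settle whether full-dose continuation after a DLT, or continuation after a non-reversible DLT, is allowed. Its wording on ending participation and removal from study contradicts its own follow-up rule.

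The impact is low to moderate. It falls on patient handling and, on the literal reading only, on Stage 1 PFS and OS follow-up. A reader might infer that the DLT endpoint or the dose selection is in doubt. The documents do not support this, because DLT counts, escalation and the MTD depend only on the occurrence of a DLT in Cycle 1. The study is also descriptive.

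No numerical size is given. The plan states no expected DLT rate, and its DLT criteria do not sort events into reversible and non-reversible, so counting criteria would not show how many patients could be re-dosed. If no DLT occurs, the DLT part has no effect. The conclusion assumes only that the quoted texts are all current in Amendment 4.

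**What to change.** If continuation after a DLT is meant to be possible:

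- **3.7.1 (DLT definition) and 4.11.2:** replace the termination wording with *study treatment will be discontinued, except where the event is reversible and the Investigator and medical monitor agree to continuation under 4.9.2; follow-up continues per 4.6.12/4.8*.
- **Duration of Therapy:** add the same exception to the DLT bullet.
- **3.7.1 (closing paragraph) and 4.9.2:** use one set of conditions after a DLT: a reversible event, a risk/benefit rationale, agreement of both parties, and a reduced dose or changed schedule.
- **4.9.1:** replace the removal wording with *discontinued from study treatment; follow-up continues per 4.6.12/4.8*.

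If discontinuation is meant to be mandatory, delete the mention of DLTs from the closing paragraph of 3.7.1 and from 4.9.2. The change from participation to treatment in 3.7.1 and 4.11.2, and the 4.9.1 change, are needed either way.

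The cost is an edit to five sections (3.7.1 in two spots, 4.11.2, Duration of Therapy, 4.9.1 and 4.9.2). No visits or data are added, because 8-weekly follow-up by telephone or site visit is already planned for all patients who stop treatment.

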reduction is permitted if clinically indicated.

In the expansion portion (Stage 2), 20 patients will be randomized in a 1:1 ratio to receive GDC-0084 either under fasted or fed conditions.

Statistical Analysis

Analysis Populations:

- The Intent -to-Treat (ITT) population includes all randomized patients; ITT analyses will be conducted on the basis of the arm assigned at randomization
- The Modified Intent-to-Treat (mITT) population includes all eligible patients who received at least 1 dose of GDC-0084 and have evaluable post-baseline tumor response data;
- Safety population (SAF): All eligible patients who received at least 1 dose of GDC-0084 will be included in the safety population. Safety analyses will be conducted on the basis of initial received treatment;
- PK population: All eligible patients in the safety population who have an adequate concentration vs. time profile to determine PK parameters;
- A Per-Protocol (PP) subset will also be used to analyze endpoints of clinical benefit and will be based on study drug exposure (compliance and/or time on study drug) and major protocol deviations. The criteria for inclusion in the PP subset will be finalized and documented prior to database lock.

Timing of Analyses:

Regular cohort safety reviews will be performed as described above during Stage 1 to support dose-escalation and if necessary, de-escalation decisions.

After all patients in Stage 2 have completed one cycle of treatment or discontinued treatment, an interim analysis of safety, PK, FDG-PET and select clinical benefit endpoints will be evaluated.

A final analysis will be performed when all patients discontinue treatment and complete their End of Treatment visit. Supplemental analyses may be performed at the completion of the study but will be considered exploratory.

General Considerations:

Data from Stage 1 and Stage 2 may be summarized separately. For Stage 1 assessment, summaries will be presented by dose level and overall. For Stage 2, summaries will be presented by treatment arm (fed versus fasting) and overall. Selected safety parameters may be summarized using pooled data from the selected dose level in Stage 1 and fasted patients in Stage 2.

There may be a statistical comparison of C_{max}/AUC between fasted and fed patient data in stage 2.

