4.5 Endpoints

4.5.1 **Primary Endpoint**

The primary endpoint of this study is safety-related and is the occurrence of DLTs during the study.

Protocol Number: NVGN-0084-201

Secondary Endpoints 4.5.2

Secondary endpoints are related to both, safety and clinical benefit as listed below.

Secondary Safety Endpoints:

- Treatment-emergent AEs (TEAEs), Grade 3-5 TEAEs, serious adverse events (SAEs), fatal AEs, and TEAEs leading to GDC 0084 discontinuation or study withdrawal;
- Treatment-emergent Grade 3/4 clinical laboratory abnormalities;
- Changes and shifts from baseline in clinical laboratory, vital signs, and ECG parameters;
- Change from baseline in corticosteroid use;
- Change from baseline in LVEF;
- Change from baseline in KPS;
- Concomitant medication use;
- Adherence to the dosing regimen.

Secondary Endpoints of Clinical Benefit:

- PFS measured from first dose in the dose-escalation portion (Stage 1) or from randomization in the cohort expansion portion of the study (Stage 2) to disease progression (RANO criteria) or death due to any cause:
- OS measured from first dose in the dose-escalation portion (Stage 1) or from randomization in the cohort expansion portion of the study (Stage 2) to death due to any cause;
- TTP measured from first dose in the dose-escalation portion (Stage 1) or from randomization in the cohort expansion portion of the study (Stage 2) to date of earliest disease progression according to RANO criteria.

4.5.3 **Exploratory Endpoints**

Exploratory endpoints in this study are:

- PFS measured from first dose in the dose-escalation portion (Stage 1) or from randomization in the cohort expansion portion of the study (Stage 2) to disease progression (modified RANO criteria) or death due to any cause:
- PK parameters including area under the curve from time 0 to last measurable time point (AUC_{0-last}) and/or area under the curve from time 0 to infinity (AUC_{0-inf}), maximum concentration (C_{max}), minimum concentration (C_{min}), time to reach C_{max} (T_{max}), t_{1/2}, apparent total clearance of the drug from plasma after oral administration (CL/F), and accumulation ratio for C_{max} and AUC (fed and fasted);
- Change in FDG-PET uptake in tumor and normal brain tissue (defined as normal brain tissue with similar cell type to tissue surrounding tumor) in response to GDC-0084 in patients with measurable disease:

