5.8 Causality Assessment

The Investigator's assessment of causality must be provided for all AEs (serious and non-serious); the Investigator must record the causal relationship in the CRF, as appropriate, and report such an assessment in accordance with the serious adverse reporting requirements if applicable.

Protocol Number: NVGN-0084-201

IND Number: 112.608

The causality assessment categorization will be:

- Unrelated: If there is no relationship and/or other factors (medicinal products or underlying disease) prove an explanation. Clearly due to extraneous causes;
- Unlikely related: If the event occurs within an improbable temporal relationship, and/or in which other factors provide a more plausible explanation;
- Possibly related: If the event occurs within a reasonable time sequence, but can also be
 explained by concurrent disease, medicinal products, or chemicals and investigational
 product causality is one of other causes for the described clinical event;
- Probably related: If the event occurs within a reasonable time sequence, was unlikely to be attributed to other factors (concurrent disease, medicinal products);
- Related: If the event occurs within a reasonable time sequence and could cannot be attributed to other factors (e.g., concurrent disease, chemicals, confounding drug administration must be absent.

An Investigator's causality assessment is the determination of whether there exists a reasonable possibility that the investigational product caused or contributed to an AE; generally, the facts (evidence) or arguments to suggest a causal relationship should be provided. If the Investigator does not know whether the investigational product caused the event, then the event will be handled as "related to investigational product" for reporting purposes, as defined by the sponsor (see Section 5.12).

If the Investigator's causality assessment is "unknown but unrelated to investigational product", this should be clearly documented on study records. In addition, if the Investigator determines an SAE is associated with study procedures, the Investigator must record this causal relationship in the source documents and CRF, as appropriate, and report such an assessment in accordance with the SAE reporting requirements, if applicable.

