7.1 Cohort Review Committee

On the basis of the review of real-time safety data and available preliminary PK data from this study with GDC-0084, dose-escalation may be halted or modified by Kazia Therapeutics Limited as deemed appropriate.

Decisions regarding dose-escalation and selection will be made by a CRC including the medical monitor, recruiting Investigators, sponsor representative and any other relevant and necessary expert on as needs basis, according to the CRC charter. For dose-escalation purposes, and selection of appropriate dose levels and schedules DLT assessments and other safety/PK will be reviewed by Kazia Therapeutics Limited in consultation with the Investigators during CRC meetings.

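### The DLT definition does not name the causality category 'Related', and the safety population is limited to 'eligible' dosed patients: two wording errors that should be corrected

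*Combined protocol and SAP*

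**What the plan says.** **DLT causality.** Section 3.7.1 counts a listed toxicity in the 28-day window as a DLT if it occurs there "and assessed by the Investigator to be probably or possibly related to GDC-0084". The synopsis has the same condition: the event must "be probably or possibly related to GDC-0084". Section 4.11.2 restates the definition as "and assessed by the Investigator to be related to GDC-0084" and sends the reader to 3.7.1 for the details.

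Section 5.8 gives Investigators five categories: Unrelated, Unlikely related, Possibly related, Probably related and Related. The last is defined separately from Probably related: "Related: If the event occurs within a reasonable time sequence and could cannot be attributed to other factors".

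These counts carry weight. Section 4.5.1 states: "The primary endpoint of this study is safety-related and is the occurrence of DLTs during the study". They also drive the 3+3 rule: "When a second patient has a DLT, the MTD is determined as 1 dose level below the current dose level".

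**Safety population.** The synopsis says: "All eligible patients who received at least 1 dose of GDC-0084 will be included in the safety population". Section 6.3.1 says the same. Section 6.3.5 places every safety analysis in this population, and section 6.3.4 uses it for the primary analysis of PFS in Stage 1. Section 5.7 has patients evaluated for safety once they have had any treatment and sets no eligibility condition.

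**The concern.** On the first item, the threshold names the two lower positive categories and omits the top one. An Investigator who is certain that the drug caused a Grade 4 thrombocytopenia would choose Related, and the words of 3.7.1 would then not make that event a DLT. The omission affects both the primary endpoint and the rule that sets the dose for Stage 2. Stage 1 starts at 60 mg, above the 45 mg MTD of the phase 1 study, and two DLTs of mucosal inflammation were seen at 65 mg in that study (Risk/Benefit Analysis). DLT counts should therefore leave no room for two readings.

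On the second item, safety summaries should follow exposure. If membership depends on eligibility, a patient who took the drug and was later found not to meet a criterion leaves every safety table, along with any toxicity that patient had.

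**Working it through.** The plan has no power or error-rate figure on this point to reproduce. Its stated totals add up (12 + 20 = 32; 6 + 20 = 26; 24 + 20 = 44) and are not affected. The check compares the texts and then applies the 3+3 rule.

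**Step 1. Which 5.8 categories does each DLT text cover?**

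| Category in 5.8 | Named in synopsis and 3.7.1 | 4.11.2, 'related' as a category label | 4.11.2, 'related' as an umbrella term |
|---|---|---|---|
| Unrelated | no | no | no |
| Unlikely related | no | no | no |
| Possibly related | yes | no | yes |
| Probably related | yes | no | yes |
| Related | **no** | yes | yes |

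No text lists all three positive categories. The umbrella reading of 4.11.2 would cover them, but 4.11.2 defers to 3.7.1, where Related is missing. Section 5.8 treats unknown causality as related for reporting purposes only. That rule does not amend the DLT definition.

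**Step 2. What does one uncounted patient do under 3.7.1?** The conditions are that the event was rated Related and that the text was applied literally.

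| DLTs in the cohort | Action under 3.7.1 | Count with one omitted | Action then |
|---|---|---|---|
| 1/3 | expand, up to 6 | 0/3 | escalate |
| 2/3 | MTD one level lower | 1/3 | expand, up to 6 |
| 2/6 (33.3%, not below 1/3) | MTD one level lower | 1/6 (16.7%, below 1/3) | dose passes |
| 3/3 | MTD one level lower | 2/3 | unchanged |

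At the starting level, two DLTs among six patients would set the MTD at 45 mg. With one omitted, 60 mg passes. An omission can only lower a count, so where the decision changes it always moves toward a higher dose or further treatment at the same dose. With three DLTs, one omission leaves two and the dose still fails, so not every omission matters.

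**Step 3. What does removing one dosed patient from the safety population do?** A full Stage 1 cohort has 6 patients and a Stage 2 arm has 10.

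- Cohort with one event: 1/6 = 17%. Removing the patient with the event gives 0/5 = 0%. Removing another patient gives 1/5 = 20%.
- Arm with one event: 1/10 = 10%. The corresponding results are 0/9 = 0% and 1/9 = 11%.

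The 3+3 decisions do not use the safety population. The AE reporting rules in section 5 and the individual listings in 6.3.3 do not depend on it either. Only the summaries and the Stage 1 PFS analysis do.

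**The case against.** The strongest reply is that this is loose drafting which nobody would apply literally. Much of that stands.

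- **Section 4.11.2 is not a rival definition.** A reader might infer two definitions with no category in common, one covering Possibly and Probably related and the other only Related. The documents do not support this. Section 4.11.2 points back to 3.7.1, and lower-case 'related' is used elsewhere as an umbrella term, for instance for TEAEs related to study drug in 6.3.5. Section 5.8 itself describes causality as a reasonable possibility that the product caused or contributed to the event.
- **There are safeguards.** The sponsor performs the DLT assessments with the Investigators at CRC meetings. Section 7.1 says that for "selection of appropriate dose levels and schedules DLT assessments and other safety/PK will be reviewed" there, and the sponsor may halt or modify escalation on real-time safety data. An event judged certainly drug-caused would be before a group with authority to stop.
- **Related is a narrow category.** Section 5.8 requires that other factors and confounding drugs be absent. In patients with GBM and recent chemoradiation, few events may be rated that high.
- **Ineligible dosed patients should be rare.** Section 4.3 requires all criteria to be checked before enrollment. A reader might infer that someone who passes the lists in 4.2 could still be dropped because other sections describe the population differently. Sections 4.2.1 and 4.3 tie eligibility to those lists, and nothing says a patient who meets them is later removed.
- **Section 5.7 concerns AE grading, not analysis sets.** Section 6.3 also ranks a separate SAP above this text. That SAP is not in the document reviewed and may settle the wording.

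What does not go away is that both rules, followed as written, give the wrong answer. No text instructs the CRC to count a Related event, and no text returns a dosed ineligible patient to the safety tables.

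**Conclusion.** Both wording errors are real and should be fixed.

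**DLT definition.** On a literal reading, the most clearly drug-caused toxicities fall outside the primary endpoint and the 3+3 counts, and any resulting error favours escalation. The intended threshold is almost certainly at least possibly related, and the sponsor and CRC would probably apply it, so the practical effect is likely small. It cannot be given a number: the documents state neither the true DLT rate, nor the share of such events that would be rated Related, nor how likely a literal reading is. A reader might infer that the MTD will be set too high. The documents show only that the wording permits such an error, not that it is likely.

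**Safety population.** The restriction conflicts with 5.7 and would remove from the safety tables, and from the Stage 1 PFS analysis, any patient dosed and later found ineligible. The number should be few and is not given. In groups of 6 or 10, a single such patient is visible in the percentages. Escalation decisions, AE reporting and listings are unaffected.

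Confidence is high about the wording. It does not extend to any effect on the dose selected.

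**What to change.** 1. In the synopsis, 3.7.1 and 4.11.2, replace the causality condition with: 'assessed by the Investigator as possibly related, probably related or related to GDC-0084'. The sponsor may also wish to state how unknown causality counts toward a DLT.
2. In the synopsis and 6.3.1, define the safety population as 'all patients who received at least 1 dose of GDC-0084', and carry the same definition into the separate SAP.

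The cost is a few words in an amendment and in the SAP. No data, visits or patients are added, and the sample size stays at about 32 (26 to 44). Reported DLT or AE counts may come out slightly less favourable.
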